### **Study Protocol**

#### **Objective**

The objective was to test whether communication messages can reduce the misperception that very low nicotine content (VLNC) cigarettes are less harmful than other cigarettes.

#### **Design**

In this between-subjects experiment, participants were recruited from a panel, screened, and then eligible participants were randomized to one of four study arms, each with different communication messages: 1) Emotion-based messages about VLNC, 2) Continued-harm-framed messages about VLNC, 3) Myth-refuting messages about VLNC, or 4) Control messages about littering. In each arm, participants were exposed to three messages, and then outcomes were assessed. The primary outcome was the VLNC misperception, and secondary outcomes included quit intentions, perceived message effectiveness, perceived understandability, attention, negative affect, cognitive reactions, social interactions, and reactance.

#### **Methods**

Participants were recruited and screened by the panel provider, and then eligible participants were directed to an online survey that included the experiment. Participants were compensated for their time by the panel provider. The study was reviewed and approved by the institutional review board of the University of North Carolina at Chapel Hill.

#### **Scientific Background**

Tobacco use is the leading preventable cause of cancer and cancer deaths in the US. While most (69%) smokers want to quit, only 6% succeed in doing so each year. For many smokers, the addictiveness of nicotine makes quitting very difficult. To reduce cigarette smoking and resulting harms, FDA recently announced a comprehensive approach to tobacco and nicotine regulation that includes moving toward a very low nicotine content (VLNC) standard for cigarettes. Greatly reduced nicotine levels would facilitate smoking cessation. However, smokers only benefit from a VLNC policy if they quit. The success of the policy may require public understanding that, although these new cigarettes are less addictive, their high toxicity and carcinogenicity are unchanged. Although communication research suggests it is challenging to change people's incorrect understanding, new communication techniques may help reduce the VLNC misperception.

### **Statistical Analysis Plan**

1,253 participants completed the study questionnaire, and the panel provider determined that of those, 1,145 qualified participants completed the questionnaire. The panel provider removed 13 cases from the study who skipped half or more of the survey questions. The study team received data for 1,132 participants. For analysis purposes, we excluded anyone who did not complete the questions for the primary outcome ( $n=79$ ), yielding a final analysis sample size of 1,053. For the analyses presented in on [clinicaltrials.gov](https://clinicaltrials.gov), we computed the outcome values for each study arm, including simple mean values for scale items. Responses from participants who did not complete all items within a scale were not included in the analyses for that scale. No

adjustments were made for testing multiple variables. Future analysis to examine statistically-significant difference between study arms for each outcome will be conducted under the supervision of a trained statistician and following best practices in statistical methods. Since the purpose of the experiment was to reduce the misperception that low nicotine cigarettes are less harmful, we may also dichotomize the outcome to determine the percentage of participants who hold the misperception in each study arm after the communication intervention.

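### The exclusion of 79 participants for incomplete primary-outcome questions appears to govern the secondary outcomes too, where it can only discard usable responses; the likely effect is small

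*Combined protocol and SAP*

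**What the plan says.** The Statistical Analysis Plan section traces the participant flow. After the panel provider's screening, "The study team received data for 1,132 participants". The next step is the exclusion at issue: "For analysis purposes, we excluded anyone who did not complete the questions for the primary outcome" (79 people), "yielding a final analysis sample size of 1,053". No other analysis sample is defined.

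The section then gives a second missing-data rule, applied scale by scale: "Responses from participants who did not complete all items within a scale were not included in the analyses for that scale".

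The Design section names one primary outcome, the VLNC misperception, and eight secondary outcomes. It also fixes the timing: "In each arm, participants were exposed to three messages, and then outcomes were assessed". Completing the primary questions is therefore a response observed after randomisation and after the messages.

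The values computed so far are descriptive, by arm. Testing between arms is left to future analysis.

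**The concern.** Two missing-data rules stand side by side, and one seems to make the other unnecessary. A participant with an incomplete primary scale is already left out of the primary analysis by the scale-level rule. A global exclusion on the same ground then has nothing left to do for the primary outcome. Its only further effect would be on the secondary outcomes, where it would drop people who answered a secondary scale in full but missed a primary question.

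Two things are at stake. The first is precision: usable secondary data are set aside with no gain elsewhere. The second is selection: each secondary comparison is restricted according to a post-randomisation response to a different outcome, which the secondary analysis does not need.

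**Working it through.** **Inputs from the Statistical Analysis Plan section.** 1,145 qualified completers; 13 removed by the panel provider; 1,132 received; 79 excluded; 1,053 analysed.

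**Reproducing the plan's figures.** 1,145 − 13 = 1,132 and 1,132 − 79 = 1,053, both exact. Share excluded: 79/1,132 = 6.98%, or 7.0%.

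**What each rule does to the 79.**
- Primary outcome, taken as one scored measure: the scale-level rule alone removes all 79, so the global exclusion adds nothing. The same holds for a single item, which cannot be analysed if missing.
- Each secondary outcome: the scale-level rule alone keeps any of the 79 who completed that scale. The global exclusion removes them.

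**How many secondary responses are lost.** The documents do not say. The provider had already acted on heavy skipping: "The panel provider removed 13 cases from the study who skipped half or more of the survey questions". Each of the 79 therefore answered more than half of the survey. But "eligible participants were directed to an online survey that included the experiment", so the survey may hold other questions, and this does not show which outcome items the 79 answered. The range is 0 to 79 per outcome.

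**Precision cost for a secondary outcome.** Let f be the share of the 79 with that scale complete, and assume that all 1,053 have it complete. The standard error under the exclusion, relative to using everyone with the scale, is √((1,053 + 79f)/1,053):

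| f | Available n | SE ratio |
|---|---|---|
| 0 | 1,053 | 1.000 |
| 0.5 | 1,092.5 | 1.019 |
| 1 | 1,132 | 1.037 |

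**Detectable difference between two arms.** Arm sizes, alpha and power are not given. Assume four equal arms, two-sided alpha 0.05 and 80% power (multiplier 2.802).
- At 1,053: 263.25 per arm, SE = √(2/263.25) = 0.0872 SD, detectable difference 2.802 × 0.0872 = 0.244 SD.
- At 1,132: 283 per arm, SE = √(2/283) = 0.0841 SD, detectable difference 2.802 × 0.0841 = 0.236 SD.

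Equivalently, a contrast with 80% power at 1,053 would have about 82.8% at 1,132. This is the most that could be recovered.

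**The case against.** The strongest reply is that the redundancy rests on two readings the SAP does not state: that the 1,053 governs the secondary outcomes, and that the primary questions form one scored measure. This stands. If the primary questions were analysed one by one, the exclusion would have a real effect on the primary analysis, although that effect would be to discard answered primary items. If the 1,053 was meant for the primary outcome only, one clarifying sentence settles the matter.

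A second reply is that a common sample across outcomes is a defensible choice. The SAP does not give this reason, and its scale-level rule already lets n differ by outcome, so the exclusion does not deliver a common sample.

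A third is that between-arm testing is deferred, so the power figures concern comparisons not yet specified. That is fair, and it is why they are only illustrations. But nothing says the 79 will be restored for those tests.

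A fourth is that the proposed rule still conditions each secondary analysis on a post-randomisation response, namely completion of that scale. This also stands: the change removes dependence on a different outcome, not complete-case selection as such.

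A reader might go further and infer that the primary result is biased because the 79 are not shown by arm. The documents do not support that. Skipping that depends on arm alone does not bias complete-case arm means; non-responders must also differ from responders within arms in a way that does not cancel between arms. With an even split (7.0% missing per arm, equal arms assumed), a bias of one standard error needs the gap between observed and missing means to differ between arms by 0.0872/0.0698 = 1.25 SD. An uneven split could lower that hurdle, but nothing in the documents points to one. Nor does silence in this document show that arm-level counts go unreported elsewhere.

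**Conclusion.** The point holds as a minor inefficiency and ambiguity in the analysis-set rule, with moderate confidence. If the primary outcome is one scored measure and the 1,053 applies throughout, the global exclusion brings no benefit to the primary analysis and may discard between 0 and 79 complete responses per secondary outcome. At the ceiling, standard errors are 3.7% larger than needed and the detectable difference is 0.244 rather than 0.236 SD (equal arms, two-sided alpha 0.05 and 80% power assumed). At the floor nothing is lost. Secondary comparisons are also conditioned on a response to another outcome, with an effect that cannot be sized from the documents. No finding of bias or of imbalance between arms follows.

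**What to change.** Reword the exclusion so that it applies to the primary outcome only. Analyse each secondary outcome in all of the 1,132 participants who completed that scale, under the scale-level rule already in the SAP. Make the change before the planned between-arm tests.

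The cost is one sentence of SAP wording and a re-run of the secondary summaries on data already held. The downside is that n varies by outcome, which the existing rule already allows.

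As a reporting addition, show the 79 by arm beside the primary result; this takes one row of counts.

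The change leaves the analysis complete-case. It does not address missing primary-outcome data, and it does not recover the 13 removed by the panel provider or anyone randomised who did not finish the questionnaire.

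### Scales are scored as item means, yet one blank item removes a participant from that scale, so calculable secondary-outcome scores are discarded and the number scored can vary between outcomes

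*Combined protocol and SAP*

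**What the plan says.** All the relevant text is in the Statistical Analysis Plan section, apart from the list of outcomes.

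- Scoring: "we computed the outcome values for each study arm, including simple mean values for scale items".
- Partly answered scales: "Responses from participants who did not complete all items within a scale were not included in the analyses for that scale".
- Survey-level removal: "The panel provider removed 13 cases from the study who skipped half or more of the survey questions". This threshold applies to the whole questionnaire, not to a scale.
- Primary outcome: a separate sentence says that "we excluded anyone who did not complete the questions for the primary outcome". That removes 79 people, "yielding a final analysis sample size of 1,053".
- Outcomes the scale rule could touch: the Design section says that "secondary outcomes included quit intentions, perceived message effectiveness, perceived understandability, attention, negative affect, cognitive reactions, social interactions, and reactance". It does not say which of these eight are multi-item.

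The documents contain no rule for scoring a partly answered scale, no imputation, no sensitivity analysis for incomplete scales, and no count of participants scored per scale.

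**The concern.** An unweighted item mean stays on the response range of its items whether it is taken over all of them or over most of them. Someone who answers five of six items therefore has a calculable score, but the plan treats that person like someone who answered none. No reason is given.

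Two things follow for any multi-item secondary outcome. Precision is given up where near-complete answers exist, and more so on longer scales, because the chance of at least one blank rises with the number of items. The rule also works scale by scale, so results for different outcomes may describe different subsets of the 1,053. With no counts by scale and arm, a reader could not see whether this happened.

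Outcomes are measured after randomisation and message exposure, so any loss of participants at scoring occurs after randomisation. That is a further reason to keep the loss small and visible.

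**Working it through.** **Step 1. Reproduce the stated flow.** Inputs, all from the Statistical Analysis Plan section: "1,145 qualified participants completed the questionnaire"; 13 removed at survey level; "The study team received data for 1,132 participants"; 79 excluded on the primary outcome.

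- 1,145 − 13 = 1,132, as stated.
- 1,132 − 79 = 1,053, as stated.
- Primary-outcome exclusion: 79 / 1,132 = 7.0%. With the survey-level removals: (13 + 79) / 1,145 = 92 / 1,145 = 8.0%.

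The counts are consistent, and they show that questions could be left blank. They do not show how many blanks remain among the 1,053.

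**Step 2. Loss under the all-items rule.** Items per scale (k) and the probability of skipping an item (q) are assumptions; the documents give neither. With independent skips, the share dropped is 1 − (1 − q)^k.

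| k | q | Share dropped | Scored of 1,053 |
|---|---|---|---|
| 4 | 1% | 1 − 0.99^4 = 3.9% | 1,012 |
| 4 | 2% | 1 − 0.98^4 = 7.8% | 971 |
| 6 | 1% | 1 − 0.99^6 = 5.9% | 991 |
| 6 | 2% | 1 − 0.98^6 = 11.4% | 933 |

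A standard error scales as 1/√n. These losses would widen it by a factor of 1/√0.961 = 1.02 in the first row and 1/√0.886 = 1.06 in the last.

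**Step 3. Loss under a half-items rule, at q = 2%.**

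- Four items: the score is missing only if at least three are blank. 4 × 0.02^3 × 0.98 + 0.02^4 ≈ 0.00003, or 0.003%.
- Six items: the score is missing only if at least four are blank. The leading term is 15 × 0.02^4 × 0.98^2 ≈ 0.000002, below 0.001%.

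Under independence, nearly all the dropped scores are recovered.

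**Step 4. Clustering.** Independence is the assumption most favourable to the change. At the other extreme, anyone who skips one item of a scale skips them all. The loss is then q itself, 1% to 2%, whatever the length of the scale, and a half-items rule recovers none of it. The truth lies somewhere between.

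**Step 5. Is 1% to 2% a reasonable range?** Suppose all 79 primary-outcome exclusions came from independent single-item skips. Then q = 1 − (1 − 0.0698)^(1/k), which is 2.4% for three questions, 1.8% for four and 1.2% for six. The number of primary-outcome questions is not given, nor how many of the 79 answered some of them. This is a plausibility check, not an estimate.

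**Step 6. Where the rule bites.** Anyone who did not complete the primary-outcome questions is already outside the 1,053, so within that sample the scale rule removes nobody further from the primary outcome. It also has no effect on single-item outcomes. Its reach is the multi-item secondary outcomes.

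**The case against.** The strongest reply is that complete-items scoring is a recognised convention, openly stated, applied uniformly and consistent with the rest of the section. The half-items threshold is equally a convention and appears nowhere in the documents. The loss is hypothetical: the 1,053 have already been filtered for heavy skippers and primary-outcome non-completers, so those who remain may skip little. The computation described is for arm-level values posted to the registry; significance tests between arms are left to later work, so no test or conclusion in the documents is shown to change.

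Much of this stands. The plan contains no arithmetic error or contradiction here, and the size of the loss is unknown. The deferral of testing, however, also favours the change, because the rule can be settled before those tests are run.

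A reader might also infer three stronger things that the documents do not support:

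- That every multi-item outcome is in fact reported on a smaller, different group. Without per-scale counts this is possible, not shown.
- That people who answer every item differ in attention or reactance, so the rule selects on the outcomes themselves. The Design section lists these only as outcomes assessed after the messages; nothing links them to completing the survey.
- That averaging the answered items cures message-dependent skipping. It does not. If a message leads people to skip particular items, the mean of the rest omits those items and can be biased by arm too.

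**Conclusion.** The point holds as one of avoidable data loss and an unreported, possibly shifting denominator on multi-item secondary outcomes. The size is undocumented. Under assumed independent skips of 1% to 2% per item, it would be about 4% to 8% of participants on a 4-item scale and 6% to 11% on a 6-item scale. It would be smaller with clustering, down to 1% to 2% with nothing recoverable in the extreme case.

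It would be tempting to conclude that the scale rule costs primary-outcome data within the 1,053. It does not: those people were removed by a separate sentence, and the documents do not say whether any of the 79 gave enough answers to be scored. Nor do the documents show that any arm comparison is biased. The change is worth making because it is cheap and checkable on data already held.

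**What to change.** For the planned between-arm analyses, replace the all-items sentence with wording such as:

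> Each multi-item secondary scale is scored as the mean of the answered items, after aligning item direction, when at least half of its items are answered (both items for a two-item scale). Otherwise the score is missing. Scoring that requires all items is repeated as a sensitivity analysis. The number of participants scored is reported for each scale and arm.

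The SAP should also state how many items each outcome has, so that a reader can see where the rule applies. For two-item scales it leaves current practice unchanged.

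If the primary outcome is multi-item, apply the same rule to the sentence that excludes the 79, recompute the 1,053, and label this as a post hoc change, since the data have already been received and the exclusion already made. Changing only the scale sentence would leave the primary and secondary outcomes under conflicting rules.

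The cost is a short SAP edit, a re-run of the scoring code on data in hand and a table of counts. If the primary exclusion changes, the participant flow must be revised as well. The downside is that a person's mean assumes the skipped items resemble the answered ones, and it does not remove bias if skipping depends on the message. The sensitivity analysis shows whether the results depend on the scoring rule, and the counts by arm show whether incomplete answering differs between arms. Neither proves that such bias is absent.

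### Does leaving the between-arm test open after the per-arm values were computed make the primary conclusion unreliable?

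*Combined protocol and SAP*

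**What the plan says.** The Design section states that "eligible participants were randomized to one of four study arms": three kinds of message about very low nicotine cigarettes, and a control arm shown messages about littering. It names a single primary outcome: "The primary outcome was the VLNC misperception". The Objective section gives the direction: "The objective was to test whether communication messages can reduce the misperception".

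The Statistical Analysis Plan is written after data collection. It gives the participant flow and says of the registry results that "we computed the outcome values for each study arm, including simple mean values for scale items". Testing comes later: "Future analysis to examine statistically-significant difference between study arms for each outcome" is to be done "under the supervision of a trained statistician and following best practices in statistical methods". The section ends by saying that "we may also dichotomize the outcome to determine the percentage of participants who hold the misperception in each study arm".

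No section names the test, the contrast, alpha, a multiplicity rule for the future tests, or the score at which a participant counts as holding the misperception. The remark that no adjustment was made is in the past tense, sits with the registry summaries and concerns multiple variables, so it sets no rule for the later comparisons.

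**The concern.** The order of events is the worry. The arm means exist, and the test that will be used to claim an effect has not been written down. Three things are open: which arms are compared, how error is controlled, and whether the outcome is a mean or a percentage. Supervision by a statistician says who will decide, but not what will be decided or when.

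If the contrast or the form of the outcome were chosen because it looked favourable, a message could be reported as effective at p<0.05 with a true false-claim rate above nominal, and a reader could not tell.

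**Working it through.** **Inputs from the documents.** Four arms, one of them control; one primary outcome; 1,053 analysed. The flow reproduces: 1,145 − 13 = 1,132 and 1,132 − 79 = 1,053. There is no stated power, alpha, standard deviation or scale to reproduce.

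**Assumptions, not in the documents.** No true effect, equal arms (1,053/4 = 263.25 each), a normal score, and unadjusted two-sided 5% tests. A false claim of benefit is then z < −1.96, so the reference value is 2.5%, not 5%.

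**1. One contrast, mean score only.** P(z < −1.96) = 2.5%. Having seen the arm means changes nothing if this is the analysis that is run and reported.

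**2. One contrast, mean or one dichotomised version, whichever succeeds.** If a proportion p holds the misperception and q is the matching normal quantile, the two test statistics have correlation φ(q)/√(p(1−p)).
- p = 0.5: 0.3989/0.5 = 0.798
- p = 0.3 or 0.7: 0.3477/√0.21 = 0.759

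The chance that at least one is favourable is 0.025 + 0.025 − P(both).
- p = 0.5: 0.05 − 0.0109 = 0.0391
- p = 0.3 or 0.7: 0.05 − 0.0098 = 0.0402

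This freedom therefore moves 2.5% to about 4%, and only if the two forms are treated as interchangeable.

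**3. Three contrasts, mean only.** The three z statistics share the control arm, so each pair has correlation 0.5. P(at least one < −1.96) = 6.3%, or 12.6% counting either direction. This figure would be identical if three unadjusted contrasts had been fixed before enrolment. It measures ordinary multiplicity, not choice after seeing results.

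**4. Cost of adjusting, if wanted.** The standard error in SD units is √(2/263.25) = 0.0872. The difference detectable with 80% power is (1.96 + 0.8416) × 0.0872 = 0.244 SD unadjusted. With the Dunnett critical value it is (2.348 + 0.8416) × 0.0872 = 0.278 SD. Dunnett on the mean brings the 6.3% back to 2.5%.

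**5. How open the choices are on the text.**
- *Contrast.* One arm is labelled control and the objective is to reduce the misperception. Each message against control is the natural reading, though it is not written as a rule.
- *Outcome form.* The percentage is introduced as something the team may *also* compute, to describe each arm. No test of it is mentioned, and nothing says it would displace the mean.
- *Cut-point.* The Objective section defines the misperception as believing these cigarettes to be less harmful than others. That anchors the dichotomy in substance, even without a numeric cut.

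**The case for a change.** The strongest opposing case is that the documents show no earlier rule, that the arm values came first, and that the percentage has neither a rank nor a cut-point. An analyst who tried everything could inflate error well beyond 4%. Under the same assumptions, the mean or the best of three cuts (at 30%, 50% and 70%) gives 6.5% for one contrast and 15.5% across three messages. Writing the rule down would cost only wording.

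Part of this stands. The contrast, error rule and cut-point are undocumented here, and a reader of a later report should look for all three message-versus-control results with confidence intervals.

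The larger figures do not carry over to this trial. They assume a search over cut-points that the documents do not describe, on a scale that they do not give, with any success reported as primary. The three-message figure also includes the ordinary multiplicity of step 3. The documents show neither a data-driven choice nor the absence of an earlier dated plan.

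The gain from new wording is also small. It would have to be declared as written after the arm values were known, so it could not recover pre-specification. It would leave adjustment across three distinct message types to judgement, because testing each comparison at its own level with all three reported is defensible.

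**Conclusion.** The observation is accurate, but it describes missing detail and not an error. A statistician comparing each message with the labelled control on the mean misperception score, and reporting all three contrasts, would reach a sound conclusion from this plan as it stands.

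The freedom that can be tied to the plan's own wording is the mean versus one dichotomised version. It would raise the one-direction false-claim chance for one contrast from 2.5% to about 4%, and only if the percentage were used as a substitute, which the text does not say. The 6.3% for three messages is ordinary multiplicity. Removing it is a trade-off against a detectable difference of 0.278 SD instead of 0.244 SD. All these figures rest on an assumed normal score, equal arms and two-sided 0.05, none of which the documents give. No change to the plan follows.
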